## INTRODUCTION

Allogeneic stem cell transplantation (HSCT) represents a fundamental therapeutic option for patients affected by malignant hematological diseases. One of the major life-threatening complication after HSCT is acute graft versus host disease (aGvHD), especially when gastrointestinal tract is extensively involved. All grade aGvHD occurred in 40-80% of HSCT recipients, depending on donor choice, stem cell source, conditioning regimen and GvHD prophylaxis. Among patients with aGvHD, intestinal involvement accounts for 60% of the cases (1). Approximately one third of patients with intestinal aGvHD reached a grade III-IV stage with an increased risk of mortality and morbidities. The most common symptom of GI involvement of acute GVHD is diarrhea, secretory and usually voluminous, often reaching more than 1.5 liters per day. In severe cases, patients presented abdominal pain and gastrointestinal bleeding may occur, reflecting the mucosal ulceration (2). These symptoms are nonspecific given the fact they might be frequently observed after allo-SCT in *Clostridium difficile* colitis, bacterial colonization, cytomegalovirus or adenovirus infection, drug toxicity, or neutropenic enterocolitis (3). Weber et al (4) reported the use of contrast enhancement ultrasound imaging (CEUS) in diagnosing gastrointestinal aGvHD. The penetration of intravenous injected contrast microbubbles into the gut lumen showed a sensitivity of 92.9% and specificity of 94.4% for intestinal aGvHD diagnosis, but the specificity was only of 39.6% for advanced stage. On the other hand, sonographic criteria

such as free fluid, bowel wall thickness, color-coded Doppler sonography (CCDS), and compound elastography showed additional modifications in severe gastrointestinal GvHD. Also Schreyer et al (5), reported transmural penetration of intravenous applied microbubbles during CEUS as feasible diagnostic feature for intestinal aGvHD involvement. Contrary to nonspecific bowel wall thickening or free fluid observation, transmural penetration of contrast microbubbles allows to discriminate between aGvHD and chronic inflammatory bowel diseases, that were used as comparing group. Benedetti et al (6) were inspired by the findings of neovascularization detected in aGvHD intestinal biopsies. They observed abnormal bowel wall thickening in multiple bowel segments, due to mucosal edema, as documented also in intestinal infectious conditions. The addition of CEUS imaging revealed microcirculation enhancement of the bowel walls during arterial phase, followed by a prolonged venous phase washout. They also monitored patients' response to treatment and noted that in patients with complete response, the picture return to be normal, both with conventional ultrasound and CEUS. In patients obtaining a partial response, ultrasound showed normal bowel wall, while CEUS still detects microvascular changes at a capillary level suggesting persistent inflammatory activity.

Ultrasound evaluation on bed-side may represent a reliable tool for aGvHD diagnosis in patients with intestinal symptoms. Even if histological features is considered the gold standard for aGvHD diagnosis, a very probable diagnosis of aGvHD could be made quickly with ultrasound method allowing to start steroid treatment with more safety if compared to the only clinical suspicion. Patients with gastrointestinal aGvHD need to be promptly

diagnosed and treated given the high rate of mortality due to advanced staged disease.

Ultrasound method might reduce time spent awaiting endoscopic and histological diagnosis, especially if will be confirmed a discriminating power of ultrasound for aGvHD rather than others intestinal complications.

In the concept of multiparametric ultrasound study of the intestine of these patients we would also like to introduce the use of shear wave elastography (SWE).

Shear wave velocity US or shear wave elastography is another ultrasonographic method for measuring tissue stiffness. Instead of direct pressure, it applies energy to the tissues through a pulse wave generated by the US probe. These vibrations displace tissue across multiple geometrical planes instead of only deforming it perpendicularly. They are propagated through tissues as a shear wave, which travels faster in denser and stiffer materials.

The literature reports various experiences on the use of SWE in the study of the intestine, especially in patients with chronic inflammatory bowel diseases (7-9). But no data are reported on the use of the method in patients with graft versus host disease. Considering the simplicity of the method, we think it can be applied to an ultrasound study of the intestine to try to understand the potential of SWE to further define the characteristics of the intestinal segments involved.

## OBJECTIVES

### *Primary objective*

Primary objective of the study is to evaluate the use of bed-side multiparametric ultrasound study in the diagnosis of gastrointestinal aGvHD in patients underwent to allogenic transplant.

### *Secondary objectives*

Secondary objective of the study is to evaluate the use of bed-side multiparametric ultrasound study in distinguishing complications different from aGvHD (i.e., infectious, drug-related o neutropenic colitis) in patients underwent to allogenic transplant as compared to auto-transplant.

Fondazione Policlinico Universitario Agostino Gemelli IRCCS  
Università Cattolica del Sacro Cuore

Dipartimento diagnostica per immagini, radioterapia oncologica ed ematologia  
Area Ematologica

## METHODS

### *Study design*

This is an ambispective interventional study with device.

### *Setting*

The study will be realized at Fondazione Policlinico Universitario Agostino Gemelli IRCCS in Rome.

### *Study duration*

The enrollment will be start after ethic committee acceptance and will enroll during a period of 12 months. Patients will be enrolled consecutively. Data will be collected prospectively during the study course and until all patients will reached 100 days after HSCT. Data will be analyzed subsequently throughout a period of six months.

Fondazione Policlinico Universitario Agostino Gemelli IRCCS  
Università Cattolica del Sacro Cuore

Dipartimento diagnostica per immagini, radioterapia oncologica ed ematologia  
Area Ematologica

## *Population*

Study population will include all patients submitted to allogenic stem cell transplantation who developed diarrhea > 500 ml per day suggestive for aGvHD until 100 days from transplant date. Patients submitted to autologous stem cell transplant who developed diarrhea between transplant date and engraftment achievement will constitute control population as for other infectious complications assessment.

## *Inclusion criteria*

- Age  $\geq 18$  years;
- Submitted to first allogeneic stem cell transplant during the 12 months period of enrollment of the study;
- Diarrhea onset until day +100 from transplant ;
- Signed informed consent.

## *Exclusion criteria*

- Previous allogeneic stem cell transplantation;
- Patients refusing to sign informed consent for the study;
- Patients affected by severe cardiomyopathy and respiratory distress/insufficiency;
- Patients unable to fully understand and accept study protocol for various problems.

### *Variables and Procedures*

Within 24-48 hours from symptoms, onset full panel of stool cultures will be performed together with Clostridium toxin assessment. Multiparametric ultrasound study will be performed at the onset of the symptoms and then weekly to monitoring intestinal changes accordingly to symptoms evolution during treatment. In the case with high suspicion for aGvHD (stool culture negative, persistent or progressive diarrhea, ultrasound imaging closely suggestive for aGvHD), as per common clinical practice, colonoscopy will be required to evaluate internal macroscopy features of the bowel and to obtain histological samples for conclusive diagnosis. In the meantime steroid therapy will be started, as per common clinical practice. The only modification of this protocol to common clinical practice is represented by the addition of a non-invasive bed-side method of evaluation of the patients with diarrhea. None of the routinely performed diagnostic and therapeutic process will be modified.

All patients submitted to autologous stem cell transplant who developed diarrhea between transplant date and engraftment achievement will constitute control population. Also in this case full panel of stool culture and clostridium toxin assessment will be performed at the onset of the symptoms. Multiparametric ultrasound study will be made at symptoms onset and then weekly until symptom resolution.

Multiparametric ultrasound study will be performed by expert qualified staff as following:

The examinations will be performed at patient's bed, in supine position, with a MyLab™9 Platform (Esaote, Italy) system. Fasting is required.

US for bowel requires both low-frequency convex probes (3.3-5 MHz) and high-frequency (5–17 MHz) linear assay probes to increase the spatial resolution of the intestinal wall and to assess the wall diameter and wall layer.

The following ultrasound parameters will be collected:

- Intestinal wall thickening (normal values < 3 mm; a mean of two measurements for section will be taken, in longitudinal and transverse sections).
- Intestinal wall stratification;
- Intestinal wall flow at colorDoppler;
- Strictures;
- Free fluid (FF) within the peritoneal cavity;
- Enlarged mesenteric lymph nodes;
- Mesenteric hypertrophy.

The contrast agent is administered intravenously and excreted through the lungs without risk of nephrotoxicity or ionizing radiation as in the case of computed tomography contrast agent; it does not remain in the body longer than 15 min. It consists of microscopic bubbles of gas (size 3–5  $\mu\text{m}$ ), which are encapsulated in a shell of flexible and stiff phospholipids: they enhance the backscatter signal from blood cells, oscillating when exposed to a low-intensity US field, thereby demonstrating tissue perfusion in real-time “blood-pool”

imaging. SonoVue (SV, Bracco, Italy) is actually the second-generation US contrast agent used for CEUS, consisting of phospholipid-stabilized microbubbles filled with sulphur hexafluoride. The recommended dose of SonoVue is 2.4 mL. Every injection should be followed by a flush with 5-10 mL of 9 mg/mL (0.9%) sodium chloride solution. Approximately, 10–15 s after intravenous injection, the SonoVue arrives to the intestinal wall, thereby achieving the maximum concentration (peak intensity) after approximately 30 s. This stage is followed by a venous phase, and it is finally excreted by the lungs. No adverse event was reported with SonoVue use: the only contraindication is severe cardiomyopathy (7-9).

The following CEUS parameters will be collected:

- Time-intensity curve (TIC) included basic intensity (B), wash-out slope and/or decent slope (K), wash-in slope or rise slope (C), time to peak (TTP), area under the gamma curve (Area), arrive time (ATM), peak intensity (PI), change of peak intensity (I).
- Any exam will be recorded;
- Acquisition time: 5'

Moreover, each single evaluation will be completed with the use of SWE in order to further evaluate the characteristics of the inflammatory bowel.

SWE of the bowel wall will be performed according to manufacturer guidelines

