## ENDPOINTS

### *Primary endpoint*

Primary endpoint of the study is to evaluate the accuracy of bed-side multiparametric ultrasound study in the diagnosis of gastrointestinal aGvHD in patients underwent to allogenic transplant in terms of sensitivity, specificity, positive predictive value (PPV) and negative predictive value (NPV).

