## STATISTICAL ANALYSIS PLAN

### *Sample Size calculation*

The literature reports various experiences on the use of SWE in the study of the intestine, especially in patients with chronic inflammatory bowel diseases. But no data are reported on the use of the method in patients with graft versus host disease. Hence, we consider this as a pilot study. As such, no formal sample size calculation is needed. However, based on common rules on pilot studies [10], the minimum sample size required would be of 20 subjects. In our department, given the median annual number of allogenic stem cell transplant, we plan to enroll 75 patients. As for the secondary endpoints, an equal number of age-matched patients undergone to autologous transplant will be enrolled.

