### *Statistical Analysis*

All variables included in the study will be first analyzed by descriptive statistic techniques. In depth, qualitative variables will be described as absolute and relative percentage frequencies. The Shapiro Wilk's test will be used to assess the distribution of quantitative variables. Data will be then expressed either as mean and standard deviation (SD), whether normally distributed, or as median and interquartile range (IQR), otherwise.

Between groups differences (allogenic vs. autologous transplant) will be assessed by the Fisher exact test and the Chi-square test, with Yates correction, as appropriate, in the case of qualitative variables. Quantitative data, indeed, will be assessed either by the Student's t test or the non-parametric Mann Whitney U test, as appropriate.

Receiver Operating Curve (ROC) analysis will be used to assess the accuracy of multiparametric bedside ultrasound in aGvHD diagnosis as compared to the histologic diagnosis (gold-standard, used as reference). Positive (PPV) and Negative predictive values (NPV), sensitivity and specificity will be computed, as well as the area under the ROC curve (AUROC).

To assess potential associations between bed-side multiparametric ultrasound measurements and aGvHD diagnosis in patients underwent to allogenic transplant uni- and multivariable logistic regression models will be used.

Logistic regression models will be also applied to assess whether bed-side multiparametric ultrasound (US) measurements differ in distinguishing complications different from aGvHD (i.e., infectious, drug-related or neutropenic colitis) in patients underwent to allogenic transplant as compared to auto-transplant. More in depth, to evaluate the combined effects between US measurements and transplant group, multivariable interaction models will be fitted, and the interaction odd ratios (IOR) evaluated. In particular, for each US measurement, one interaction logistic regression model will be fitted. In summary, the coefficients of the main effects (in exponential terms) will be interpreted as ORs of the outcome by considering the allo-transplant group from control ( $OR_{\text{autologous}}$ ), by

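### A suggestive ultrasound helps trigger the biopsy that serves as reference standard, and no masking or order of reading is specified, so review bias in the accuracy estimates cannot be excluded

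*Combined protocol and SAP*

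**What the plan says.** Variables and Procedures sets out when the reference standard is obtained. The sentence opens "In the case with high suspicion for aGvHD (stool culture negative, persistent or progressive diarrhea, ultrasound imaging closely suggestive for aGvHD" and, for such cases, goes on to say that "colonoscopy will be required to evaluate internal macroscopy features of the bowel and to obtain histological samples for conclusive diagnosis". The index test is thus one of three named features behind the request for the reference test.

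The Statistical Analysis section assesses ultrasound accuracy "as compared to the histologic diagnosis (gold-standard, used as reference". The Primary endpoint section defines accuracy "in terms of sensitivity, specificity, positive predictive value (PPV) and negative predictive value (NPV".

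On readers, the protocol says "Multiparametric ultrasound study will be performed by expert qualified staff as following". On the contrast examinations it lists the time-intensity curve parameters and adds "Any exam will be recorded". The available text says nothing about what the biopsy request contains, what the pathologist or endoscopist knows, when the curves are extracted, or when the ultrasound reading is final. It gives no rule for calling the multiparametric examination positive.

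**The concern.** Two readings need to be independent, and the plan protects neither.

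- **Histology read with ultrasound known.** A clinician stating why colonoscopy is wanted would naturally mention a suggestive scan, and nothing in the text prevents it. A borderline biopsy may then be settled toward the scan. Doing the onset scan before the biopsy does not help, because that order protects the scan from the biopsy and not the reverse.
- **Ultrasound read with histology known.** Curve parameters can be taken from a recording at any later time, and the overall impression has no stated rule. Either could be settled after the histology report arrives. Weekly scans done after biopsy are open to the same influence, but they serve a secondary endpoint.

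At stake is the primary endpoint. Both routes make the two tests agree more often than they should, among patients who have both results.

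**Working it through.** The plan states no accuracy target or precision, so there is no figure of its own to reproduce. The check asks how far review bias could move the estimates.

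**Inputs from the documents.** The sample is 75 allogeneic patients ("given the median annual number of allogenic stem cell transplant, we plan to enroll 75 patients"). The Introduction cites 92.9% sensitivity and 94.4% specificity from an earlier contrast-ultrasound study. It also gives acute GvHD in 40-80% of recipients with intestinal involvement in 60% of those: 0.40 × 0.60 × 75 = 18 and 0.80 × 0.60 × 75 = 36 cases. These rates describe all recipients, not those enrolled with diarrhea, so 18-36 is only a working range.

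**Assumptions not in the documents.** A second scenario has true sensitivity and specificity both 80%. A share e of discordant results, 0.1 to 0.3, is resolved toward ultrasound. Prevalence is 0.3-0.7 where the cited accuracy is used. All patients have histology, except where stated.

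**Histology drawn toward ultrasound.** A share e of false positives (FP) becomes true positives (TP), and a share e of false negatives (FN) becomes true negatives (TN):

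- Se′ = (TP + e·FP) / (TP + e·FP + (1−e)·FN)
- Sp′ = (TN + e·FN) / (TN + e·FN + (1−e)·FP)

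With 80%/80% and 18 cases, TP = 14.4, FN = 3.6, FP = 11.4 and TN = 45.6. At e = 0.1:

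- Se′ = 15.54 / (15.54 + 3.24) = 0.827
- Sp′ = 45.96 / (45.96 + 10.26) = 0.818

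| e | 18 cases, Se′ / Sp′ | 36 cases, Se′ / Sp′ |
|---|---|---|
| 0.1 | 0.827 / 0.818 | 0.820 / 0.820 |
| 0.2 | 0.853 / 0.835 | 0.841 / 0.840 |
| 0.3 | 0.876 / 0.854 | 0.861 / 0.859 |

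From the cited 0.929/0.944, over e = 0.1-0.3 and prevalence 0.3-0.7, Se′ is 0.936-0.951 and Sp′ is 0.949-0.962.

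**Ultrasound drawn toward histology.** Here Se′ = Se + e(1−Se), and likewise for specificity. From 80%, e = 0.1 gives 0.80 + 0.1 × 0.20 = 0.82 and e = 0.3 gives 0.86. The direction is the same and the size similar.

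**If only ultrasound-positive patients are biopsied.** There are then no FN or TN among those analysed. Sensitivity is 1 and specificity 0 whatever the pathologist knows, and influenced histology changes only PPV′ = (TP + e·FP) / (TP + FP). With 80%/80% and 18 cases, PPV goes from 14.4/25.8 = 0.558 to 15.54/25.8 = 0.602 (e = 0.1) and 17.82/25.8 = 0.691 (e = 0.3). With 36 cases it goes from 28.8/36.6 = 0.787 to 29.58/36.6 = 0.808 and 31.14/36.6 = 0.851.

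**Partial verification, shown separately.** Suppose all ultrasound-positive patients but only a fraction v of ultrasound-negative patients are biopsied, with no review bias:

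- Se_v = Se / (Se + v(1−Se))
- Sp_v = v·Sp / (v·Sp + (1−Sp))

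At v = 0.10 and 0.929/0.944:

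- Se_v = 0.929 / (0.929 + 0.0071) = 0.992
- Sp_v = 0.0944 / (0.0944 + 0.056) = 0.628

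Adding review bias at e = 0.2 with prevalence 0.5 gives 0.994 and 0.681. At the same v, review bias still pushes both upward, but specificity stays well below its true value.

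**The case against.** The strongest reply is that the plan is silent, not faulty. A reader might infer that nobody is masked, or that histology is read with the ultrasound result in hand. The documents state neither. They do not describe the biopsy request, and calling the sonographers expert says nothing about masking. That part of the reply stands: the supportable statement is that masking is not specified in the available text.

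A second reply is that the quoted sentence bears more directly on who is biopsied than on how the biopsy is read. That also stands. A reader might conclude that accuracy will be overstated on every measure. The calculation does not support this, because ultrasound-triggered biopsy raises sensitivity and lowers specificity. Whether the three features must all be present is unclear, so the verified fraction is unknown.

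Third, the size is modest if accuracy is as high as the cited study reports, and the resolution rate has no source. Both are true, which is why a range is given.

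Fourth, a reader might think the bias could never be undone. Because examinations are recorded, a later masked re-read is feasible on the ultrasound side, and stored slides might allow one on the histology side. The available text plans neither.

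Pilot status does not remove the point, since the accuracy estimates are the primary output.

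**Conclusion.** The point holds as a gap in the plan. A suggestive scan is part of the indication for the reference test, and the available text neither masks the pathologist nor fixes the ultrasound and curve readings before histology is known. Review bias in the primary endpoint is therefore possible and preventable, but not demonstrated.

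Its size rests on assumptions. With full histology and 10-30% of discordant results resolved toward ultrasound, the rise is about 2-8 points in sensitivity and 2-6 in specificity from 80%/80%. From the cited figures it is about 0.7-2.2 and 0.5-1.8 points. With biopsy confined to ultrasound-positive patients, influenced histology would instead inflate PPV.

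The net direction across all measures cannot be stated, because partial verification works against review bias for specificity. That is a separate problem which masking does not solve. The change is worth making because it is cheap.

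**What to change.** Add to Variables and Procedures:

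- (a) The biopsy request gives the clinical indication without the ultrasound, contrast or elastography findings, and the study histology report is made without them.
- (b) The onset ultrasound form, including the overall reading for or against aGvHD, is completed and locked before histology is released.
- (c) Curve parameters for the primary analysis are extracted by the same staff from the recorded onset examination before histology is known.

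The treating team may still see the ultrasound. The cost is wording on the request form, a dated lock on the ultrasound form and some coordination. No extra reader or procedure is needed.

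Masking will be incomplete while ultrasound helps trigger colonoscopy, because being biopsied itself hints at a suggestive scan. The plan should separately say how patients without histology enter the accuracy analysis. It should also reconcile the use of ultrasound as a trigger with the statement that "None of the routinely performed diagnostic and therapeutic process will be modified".

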### *Data Collection*

Each patient transplanted at Hematology and stem transplant Unit of the Fondazione Policlinico Universitario Agostino Gemelli IRCCS had to provide informed consent for enrollment. Data on patients and transplant characteristics will be recorded prospectively: age, underlying disease, conditioning regimen, donor type, stem cell source, GvHD prophylaxis, diarrhea features, treatment for diarrhea, microbiological and radiological findings, ultrasound findings, endoscopic finding and histological report.

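### The scan under test helps decide who gets histology, histology is the only reference for the primary accuracy measures, and the plan has no rule for patients without it

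*Combined protocol and SAP*

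**What the plan says.** Under Variables and Procedures, every allogeneic patient with symptoms is scanned at onset and then weekly. The next diagnostic step is set out for patients with "high suspicion for aGvHD (stool culture negative, persistent or progressive diarrhea, ultrasound imaging closely suggestive for aGvHD". For them, "colonoscopy will be required to evaluate internal macroscopy features of the bowel and to obtain histological samples for conclusive diagnosis". The text does not say whether the three features must all be present or whether any one is enough. It schedules no histology for other allogeneic patients. The same section adds that "None of the routinely performed diagnostic and therapeutic process will be modified".

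The primary endpoint is accuracy "in terms of sensitivity, specificity, positive predictive value (PPV) and negative predictive value (NPV". The Statistical Analysis section assesses the "accuracy of multiparametric bedside ultrasound in aGvHD diagnosis as compared to the histologic diagnosis (gold-standard, used as reference", and adds the area under the ROC curve. It names no second or composite reference.

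Neither the Endpoints, Sample Size calculation, Statistical Analysis nor Data Collection section says whether a patient without histology is excluded, counted as free of aGvHD, or handled in another way. The supplied text also gives no rule that makes a scan positive. It lists separate B-mode, contrast and elastography parameters and plans a ROC analysis.

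**The concern.** When the result of the index test influences who receives the reference test, accuracy computed only in verified patients does not in general estimate accuracy in all patients tested. Here ultrasound-negative and culture-positive patients are less likely to reach biopsy.

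If biopsy follows mainly the scan, sensitivity is biased up, specificity is biased down, and NPV rests on few patients. If the culture result also matters, specificity can move either way, and PPV and NPV can be biased too. The planned output would not let a reader judge the size of the bias, nor its direction for specificity. Since the counting rule is unstated, it could also be chosen after the data are seen.

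**Working it through.** **Inputs.** From the documents: 75 allogeneic patients ("we plan to enroll 75 patients", set from transplant volume with no formal calculation, so there is no figure to reproduce). Everything else is assumed for illustration, because the documents give no biopsy rate, culture-positive rate, aGvHD share or design value for accuracy. The scan is treated as positive or negative. Se and Sp are true sensitivity and specificity; v1 and v0 are the shares of ultrasound-positives and ultrasound-negatives biopsied; v1 = 0.9.

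**1. Biopsy depends on the scan alone.** In verified patients:

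- observed Se = Se·v1 / (Se·v1 + (1−Se)·v0)
- observed Sp = Sp·v0 / (Sp·v0 + (1−Sp)·v1)

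With Se = Sp = 0.80:

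| v0 | observed Se | observed Sp |
|---|---|---|
| 0.9 | 80.0% | 80.0% |
| 0.8 | 81.8% | 78.0% |
| 0.5 | 87.8% | 69.0% |
| 0.2 | 94.7% | 47.1% |
| 0.1 | 97.3% | 30.8% |

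For example, at v0 = 0.2: 0.72/(0.72+0.04) = 94.7% and 0.16/(0.16+0.18) = 47.1%.

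**2. Culture also drives biopsy.** Let 40% of non-aGvHD patients be culture-positive, with specificity 60% in them and 90% in culture-negatives. True specificity is 0.4·0.6 + 0.6·0.9 = 78%.

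- Only culture-negatives biopsied: observed Sp = 0.9·v0/(0.9·v0 + 0.1·0.9). This is 83.3% at v0 = 0.5 (biased up) and 66.7% at v0 = 0.2 (biased down). The sign changes at about v0 = 0.355.
- Culture-positives biopsied at one quarter of the culture-negative rate: 76.9% at v0 = 0.5 and 57.1% at v0 = 0.2.

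**3. The counting rule.** Take 75 patients, a 50% aGvHD share, Se = Sp = 0.80, v1 = 0.9 and v0 = 0.2. Verified: TP 27, FP 6.75, FN 1.5, TN 6. Without histology: 3.75 ultrasound-positive and 30 ultrasound-negative.

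| Unverified counted as | Sensitivity | Specificity |
|---|---|---|
| all aGvHD | 30.75/62.25 = 49.4% | 6/12.75 = 47.1% |
| all non-aGvHD | 27/28.5 = 94.7% | 36/46.5 = 77.4% |
| positives non-aGvHD, negatives aGvHD | 27/58.5 = 46.2% | 6/16.5 = 36.4% |
| positives aGvHD, negatives non-aGvHD | 30.75/32.25 = 95.3% | 36/42.75 = 84.2% |

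The true 80% specificity lies outside the first two rows but inside the full bounds, so the mixed assignments are needed. If 90% of both groups are verified (TP 27, FP 6.75, FN 6.75, TN 27; 3.75 unverified in each), the bounds for both measures shrink to 27/37.5 = 72.0% and 30.75/37.5 = 82.0%.

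**4. What a correction does.** In step 3, Begg-Greenes by scan result recovers 80%/80% on expected counts. Over 200,000 simulated trials of 75, the central 95% of estimates runs from 57% to 100% for sensitivity and 62% to 93% for specificity. With full verification it is 67% to 92% for both.

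That recovery depends on biopsy following the scan alone. Take step 2 with a 50% aGvHD share, sensitivity 80%, 10% of aGvHD patients culture-positive, culture-positives biopsied at one quarter of the rate, and v0 = 0.5. Verified PPV is 0.333/(0.333+0.045) = 88.1%, and verified NPV is 0.150/(0.150+0.04625) = 76.4%. The scan is positive in 51% and negative in 49% of all patients. Begg-Greenes by scan alone gives specificity 0.764·0.49/(0.764·0.49 + 0.119·0.51) = 86.1%. The truth is 78% and the uncorrected value 76.9%, so this correction increases the error. Stratifying on scan and culture recovers 78%. If no culture-positive patient is biopsied, the scan-only correction gives 90.4%.

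**5. Sparse cells.** In step 3 only 37.5·0.2 = 7.5 ultrasound-negatives have histology. An NPV of 6/8 has an exact 95% interval of 35% to 97%. In the one-quarter setting, ultrasound-negative culture-positives number 75·0.5·(0.1·0.2 + 0.4·0.6) = 9.75. At v0 = 0.2 about 9.75·0.2·0.25 = 0.5 of them would have histology.

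**The case against.** The strongest reply is that biopsy here is routine care. The protocol describes colonoscopy as common practice and says that "None of the routinely performed diagnostic and therapeutic process will be modified". On that reading biopsy could be nearly independent of the scan, and the first rows of the table in step 1 show little or no bias. This stands as a limit on size, and those rows belong in the range. It does not remove the gap: the same section lists the scan among the features leading to colonoscopy, and any patient who misses biopsy for any reason still has no counting rule.

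A second reply is that the population is already restricted to patients "who developed diarrhea > 500 ml per day suggestive for aGvHD until 100 days from transplant date". That governs entry, whereas colonoscopy is tied to a further level of suspicion.

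A third is pilot status. It may explain the absence of a formal sample size, but accuracy is still the primary endpoint.

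It is also fair to say that a correction can do harm. Conditioning on the scan alone can add bias (step 4), and a correction by scan result cannot be run until a positive scan is defined. Both points stand and shape the fix.

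A reader might go further and infer that no ultrasound-negative patient will have histology, so that sensitivity must tend to 100% and specificity to zero. The documents do not support this. They do not say that the three features are jointly required, and routine colonoscopy or a later weekly scan may bring such patients to biopsy.

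**Conclusion.** The concern holds in this form: the scan is a listed feature leading to the reference test, histology is the only reference for every primary accuracy measure, and unverified patients are not handled. Confidence in that is high.

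Confidence in the size is moderate. Under the assumptions of step 1 the distortion runs from none to 17.3 points for sensitivity (97.3 − 80) and 49.2 points for specificity (80 − 30.8), depending on a biopsy rate that the documents do not give. A reader might also infer that specificity will necessarily be understated. That follows only if biopsy tracks the scan alone; where culture also drives it, the sign is uncertain. The matter should be settled before analysis, because a rule chosen afterwards would not be pre-specified.

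**What to change.** In the Statistical Analysis section:

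- **Denominator.** Take all enrolled allogeneic patients with qualifying diarrhea and an onset scan. First reconcile Population (more than 500 ml per day, suggestive of aGvHD) with Inclusion criteria (diarrhea onset up to day +100, no volume). Report numbers with and without histology by scan result and culture result.
- **Positive scan.** Pre-specify the rule that makes an onset scan positive.
- **Uncorrected result and bounds.** Report the histology-only result with the four assignments of step 3.
- **Correction.** Add one that conditions on both scan and culture: Begg-Greenes stratified by both where cells allow, or multiple imputation using scan, culture and symptom course. Do not use Begg-Greenes by scan alone. If cells are too sparse, rely on the bounds.
- **Limits.** If no ultrasound-negative patient has histology, state that sensitivity, specificity and NPV cannot be estimated from histology alone. If no culture-positive patient has histology, limit results to culture-negative patients.
- **AUROC.** Present it as histology-only with this caveat, or compute it from the same imputed data.

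In Variables and Procedures, reconcile the list that includes ultrasound with the statement that routine work-up is unchanged. No biopsy rule is proposed here.

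The cost is SAP text, agreement on a scan rule, and some added analysis. Data Collection already covers "microbiological and radiological findings, ultrasound findings, endoscopic finding and histological report", so no new procedure is needed. The price is wider intervals, sparse cells with 75 patients, and reliance on biopsy depending only on recorded variables.
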